#### 4.6.1. Risk Assessment

Potential Risk of Clinical Significance	Summary of Data/Rationale for Risk	Mitigation Strategy
Investigational Product (IP) : GSK1358820		
Urinary tract infections (UTI)	
As the result of integrated data with 1 completed phase 2 study (191622-077), 2 completed pivotal phase3 study (191622-095 and 191622-520) and an interim cut of the long-term extension study (191622-096), the frequency of UTI as an adverse event, which was occurred in 26.4% of patients in the 100 U BOTOX group and 10.1% of patients in the placebo group (refer to IB section 5.2.4.2 Overactive Bladder).
 
The following potential factors that may have facilitated the occurrence of UTI were:
 
 
1) Elevated PVR urine volume post treatment
 
2) Initiation of clean intermittent catheterization for bladder emptying purposes when urinary retention occurred.
 
3) Patients <math>\geq</math> 65 years are more predisposed to development of UTIs overall regardless of any treatment
 
4) Cystoscopy for study drug administration procedure (intradetrusor injection) during study participation.
 
	
Patients with potential risk for these events will be excluded from this study (refer to Protocol section 5.2 exclusion criteria 4, 5, 17 and 26 )
 
Urinalysis, urine culture and sensitivity test will be performed at each visits. If bacterial infection is confirmed, treatment with antibiotics will be administered in the opinion of the investigators/subinvestigators. The patients are not allowed to receive the injection of the investigational product until bacterial infection is negative (refer to Protocol section 7.4.6.2.Urinalysis).
 
Treatment with antibiotics will be administered to prevent bacterial infection before / after the injection of the investigational product (refer to Protocol section 6.1.2.1.Antibiotics)

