The total volume voided will be measured and recorded by subjects over one 24-hour period during the 3-day bladder diary collection period (urine volume of urinary incontinence will not be measured and recorded). To perform this measurement, urine collection containers provided by the sponsor will be used. The volume voided per micturitionb will be determined by the sponsor from the total urine volume measured by the subjects divided by the number of micturitions (excluding urinary incontinence episode).

If a subject has symptoms of a urinary tract infection, the diary data will not be collected during this period because the data may have influence on the bladder diary data.

a: used for evaluation of primary endpoint (Change from baseline in the daily average number of urinary incontinence episodes a at week 12 after the first treatment)

b: used for evaluation of major secondary endpoint (Change from baseline in the average volume voided per micturition at week 12 after the first treatment)

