#### **7.4.6.2.2. Urinalysis, Culture and Sensitivity**

Urinalysis, culture and sensitivity will be centrally performed at the central laboratory. A urine culture and sensitivity test will be performed when urinalysis results with a urine reagent strip are suggestive of a UTI (positive nitrites or leukocyte esterase) (see below for the definition of AE urinary tract infection).

If PVR at scheduled visits is  $\geq 200$  mL and an additional follow-up visit occurs 1 week later, urinalysis, urine culture and sensitivity test at the central laboratory will be performed (see 7.4.7 Post-void residual (PVR) urine volume).

- Definition of AE urinary tract infection

If both of the following criteria are fulfilled, urinary tract infection is recorded as an adverse event, irrespective of symptoms:

- 1) The result of urine culture is positive (with the presence of bacteriuria with  $\geq 10^5$  CFU/mL)
- 2) Leukocyturia with  $> 5$  per high power field is noted.

If subjects report urinary tract infection, which is diagnosed by a physician at a medical institution other than study sites (i.e., a family doctor or critical care physician), the results of urinalysis, urine culture, and sensitivity test should be obtained as far as possible.

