7.1.4. Strategy for Intercurrent (Post-Randomization) Events

Following strategy will be planned for intercurrent events. Note that these strategies will be applied for the data until 12 weeks after first administration.

Intercurrent Events	Strategy
Treatment discontinuation / Study withdrawal	
Considering the characteristics of study treatment, treatment discontinuation is not defined in this study.
 
In primary analysis, the missing data after study withdrawal will not be imputed and treated as missing. This means it is assumed that missing mechanism is missing-at-random for primary endpoint. In sensitivity analysis of assumed missing mechanism for primary endpoint, multiple imputation strategy by using placebo data (controlled imputation) will be done. This means it is assumed that missing mechanism is missing-not-at-random for primary endpoint. In this analysis. The missing data for GSK1358820 100U after treatment discontinuation will be imputed by using placebo data, while the missing data for placebo will be imputed by using placebo data. See "Handling of Missing Data for Statistical Analysis" in detail.

Use of protocol inhibited medication	
Not planned any specific handling for use of protocol inhibited medication. However, if many subjects (10% or more) used protocol inhibited medication until week12 after first treatment, additional sensitivity analysis might be done.

Intercurrent Events	Strategy
Use of rescue medication	Rescue medication is not defined in this study.

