7.1.5.1. Statistical Methodology Specification

Endpoint / Variables

 Change from baseline in the daily average number of urinary incontinence episodes at week 12 after the first treatment 
 “Daily average” means “Daily frequency calculated by 3-day dairy”. More detail for calculation methods will be in section 11.6.2
Model Specification

 The endpoint will be analyzed using a mixed model for repeated measures (MMRM). Terms fitted in the MMRM model will include: 
 Fixed, categorical effects: treatment, site, visit, treatment-by-visit interaction Fixed, continuous effects: baseline daily average number of urinary incontinence episodes, baseline-by-visit interaction An unstructured variance structure will be used to model the within-subject errors, shared across treatments. The Kenward-Roger option in SAS PROC MIXED will be used to estimate denominator degrees of freedom and standard errors.
Model Checking & Diagnostics

 The Kenward and Roger method for approximating the denominator degrees of freedom and correcting for bias in the estimated variance-covariance of the fixed effects will be used. An unstructured covariance structure for the R matrix will be used by specifying ‘type=UN’ on the REPEATED line. Akaike's Information Criteria (AIC) will be used to assist with the selection of covariance structure.
Model Results Presentation

 Adjusted means (least square means: LS means) and corresponding standard errors (SEs) of means will be presented for each treatment by visit, together with estimated treatment differences (GSK1358820 – Placebo), the corresponding 95% confidence intervals and p-values. The primary treatment comparison will be the contrast between treatments at week

12 after the first treatment.

 Plots of LS means and SEs from the model will be generated for each treatment by visit.
Data included in Model

 The dataset including only data until week 12 after the first treatment will be used.
Subgroup Analyses

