
 The above endpoints will be analyzed using the Cochran-Mantel-Haenszel test (CMH test) stratified by a stratification factor at each visit
Model Results Presentation

 The number and percent of subjects who met each endpoint will be summarized by treatment and visit. The Mantel-Haenszel estimate of common odds ratio and its 95% confidence intervals will be estimated. The p-values by CMH test will be presented at each visit. Plots of proportion of subjects attaining 100% reduction will be generated for each treatment until week 12 after 1st treatment. As same for proportion of subjects attaining $\geq 75\%$ and $\geq 50\%$ reduction will be generated.
Handling Missing Data of Change from Baseline in the urinary diary

 If a subject has missing data due to any reasons (e.g., early withdrawal), then this subject will be regarded as NOT attaining 100%, $\geq 75\%$ and $\geq 50\%$ reduction from baseline in the daily

Other Secondary Statistical Analyses for Binary data

average of urinary (urgency) incontinence episodes (i.e., regarded as a non-responder). This rule will be applied to the data until week 12 after 1st treatment. Missing data after 12 week after 1st treatment will not be imputed and treated as missing.

- This rule will be called as “DO=NR” rule. DO=NR means dropout equals to non-responder.

Other Secondary Statistical Analyses for Binary data for TBS**Endpoint(s)**

- Proportion of subjects with positive response on the TBS

Model Specification

- The above endpoints will be analyzed using the Cochran-Mantel-Haenszel test (CMH test) stratified by a stratification factor at each visit

Model Results Presentation

- The number and percent of subjects who met each endpoint will be summarized by treatment and visit.
- The Mantel-Haenszel estimate of common odds ratio and its 95% confidence intervals will be estimated.
- The p-values by CMH test will be presented at each visit.

Handling Missing Data of TBS

- Missing data due to any reasons (e.g., early withdrawal) will be regarded as no positive response. This rule will be applied to the data until week 12 after 1st treatment. Missing data after 12 week after 1st treatment will not be imputed and treated as missing.
- This rule will be called as “DO=NR” rule. DO=NR means dropout equals to non-responder.

Other Secondary Statistical Analyses for Categorical data**Endpoint(s)**

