- Change from baseline of maximum urgency intensity
- Proportions of patients with maximum urgency intensity

Model Specification

- The above endpoints will be analyzed using van Elteren test stratified by a stratification factor at each visit

Model Results Presentation

- Change from baseline of maximum urgency intensity: The number and percent of subjects who met following category will be summarized by treatment and visit.
 - 3 point improvement
 - 2 point improvement
 - 1 point improvement
 - No Change
 - 1 point worsening
 - 2 point worsening
 - 3 point worsening
- For calculation of above category, the following values will be used for each intensity
 - 0: None
 - 1: Mild

Other Secondary Statistical Analyses for Categorical data

 ○ 2: Moderate ○ 3: Severe 
 ● Proportions of patients with maximum urgency intensity: The number and percent of subjects will be summarized by maximum urgency intensity category (None, Mild, Moderate or Severe) in the visit. No statistical test will be done for this endpoint. ● The p-values by van Elteren test will be presented at each visit for change from baseline of maximum urgency intensity.
Baseline Observation Carried Forward for Missing Data

 ● Missing data until week 12 after the first treatment will be imputed by baseline observation carried forward (BOCF). This rule will be applied to the data until week 12 after 1st treatment. Missing data after 12 week after 1st treatment will not be imputed and treated as missing.

Other Secondary Statistical Analyses for Time to Event data
Endpoint(s)

 ● Time to the subject's first request for 2nd treatment from the day of 1st treatment ● Time to the subject's first qualification for 2nd treatment from the day of 1st treatment
Model Specification

 ● The above endpoints will be analyzed using the log-rank test stratified by a stratification factor. ● The above endpoints will be displayed as Kaplan-Meier curves. ● In order to estimate the hazard ratio to placebo and its 95% confidence interval, Cox proportional hazard model will be used. This Cox model include treatment and a stratification factor as fixed effect.
Model Results Presentation

 ● The p-values by log-rank test will be presented. ● The hazard ratio to placebo and its 95% confidence interval will be estimated.

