11. APPENDICES

11.1. Appendix 1: Protocol Deviation Management and Definitions for Per Protocol Population

11.1.1. Exclusions from Per Protocol Population

A subject meeting any of the following criteria will be excluded from the Per Protocol population:

Number	Exclusion Description
01	Eligibility Criteria Not Met: Subjects who have deviated from any of inclusion or exclusion criteria
02	Excluded Medication (medication excluded by the protocol was administered) : Subjects who have taken any of prohibited medication during the study.
03	Excluded Medication (device excluded medication deviation) : Subjects who have taken any of prohibited device during the study
04	Excluded Medication (other excluded medication deviation) : Subjects who have taken any of prohibited procedure during the study
05	Wrong Study Treatment/Administration/Dose: Subjects who have taken wrong study treatment

Exclusions from the Per Protocol population which are not considered to be deviations:
After the process of assessment windows for efficacy analyses (see section 11.3) is applied, the subject who has the incomplete 3-day diary [1] data (including no data of 3-day diary) at week 12 of TC1 will be excluded from the Per Protocol population.

[1] Incomplete 3-day diary is defined as the diary which does not have 3 valid diary days.
Refer to 11.6.2 for valid diary day.

CONFIDENTIAL

204947

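### Does withholding the bladder diary during urinary tract infection symptoms need a named strategy in the SAP, or symptomatic diaries as a check?

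*Protocol*

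**What the plan says.** Protocol 7.3.1.1 (Bladder diary) states: "If a subject has symptoms of a urinary tract infection, the diary data will not be collected during this period". It gives the reason, that infection may influence the diary, and its footnotes tie the same diary to the primary and the major secondary endpoint.

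Protocol 4.6.1 gives adverse-event rates for UTI: "which was occurred in 26.4% of patients in the 100 U BOTOX group and 10.1% of patients in the placebo group", pooling one phase 2 study, two phase 3 studies and an interim cut of an extension study. In this trial, by Protocol 7.4.6.2.2, when the culture and white-cell criteria are both met "urinary tract infection is recorded as an adverse event, irrespective of symptoms".

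SAP 7.1.4 lists treatment discontinuation or study withdrawal, prohibited medication and rescue medication as intercurrent events. On withdrawal it says: "In primary analysis, the missing data after study withdrawal will not be imputed and treated as missing". SAP 7.2.4 reuses the table for the major secondary endpoint. The primary model in SAP 7.1.5.1 has "Fixed, categorical effects: treatment, site, visit, treatment-by-visit interaction", plus baseline and baseline-by-visit, and no term for UTI.

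SAP 11.6.3 needs only one valid diary day in the Week 12 window, Day 65 to Day 106.

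**The concern.** The diary is withheld for a reason linked both to treatment and to the outcome. If UTI is commoner on active, more active than placebo diaries may be blank at Week 12. If infected patients leak more than the model predicts from their baseline and earlier visits, the missing values are worse than the missing-at-random analysis supposes, and leaving them out would flatter the active arm relative to an analysis of every diary as recorded.

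The SAP seems not to have noticed this. Its intercurrent-event table is silent on UTI, and SAP 11.7.3 defines an intermittent gap as Week 2 or Week 6 only, so a blank Week 12 diary in a patient still in the study is neither intermittent nor post-withdrawal. The treatment of that blank then varies by analysis, and a patient who obeyed the protocol is dropped from the per-protocol set. Since symptomatic diaries are not collected, no planned analysis can show how far the result depends on them.

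**Working it through.** **1. What happens to a wholly blank Week 12 diary**

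| Analysis | Treatment of the blank | Place |
|---|---|---|
| MMRM, primary and major secondary | left missing, assumed missing at random | SAP 7.1.4, 11.7.3 |
| Sensitivity analysis, same endpoints | imputed from a model fitted to placebo data | SAP 11.7.3 |
| Per-protocol analysis | "the subject who has the incomplete 3-day diary [1] data (including no data of 3-day diary) at week 12 of TC1 will be excluded" | SAP 11.1.1 |
| 50%, 75% and 100% responders | "If a subject has missing data due to any reasons (e.g., early withdrawal), then this subject will be regarded as NOT attaining" | SAP 7.3.5.1 |
| Maximum urgency intensity | "Missing data until week 12 after the first treatment will be imputed by baseline observation carried forward (BOCF") | SAP 7.3.5.1 |

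Every cell is filled, so no blank is left without a rule. The first three rows concern the two main endpoints and are a primary, a sensitivity and a per-protocol analysis. The last two concern other endpoints.

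**2. The plan's own power figures**

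Inputs from Protocol 9.2.1: differences of 1.79 episodes/day and 30 mL, SDs of 3.5 and 70, 120 per arm, two-sided 5%. The two-sample t-test gives 97.6% and 91.1% (stated: 98% and 91%). The Bonferroni lower bound is 97.6 + 91.1 - 100 = 88.7% (stated: 89%). The figures reproduce. Standard errors are 3.5 x sqrt(2/120) = 0.452 episodes/day and 70 x sqrt(2/120) = 9.04 mL.

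**3. Size of the gap**

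The documents give neither the share of Week 12 diaries lost to UTI symptoms nor the effect of UTI on the diary. All inputs here are assumptions. Let pA and pP be the shares lost on active and placebo, and x the excess episodes/day in a UTI diary over what the model would predict. Relative to using those diaries as recorded, the difference is (pA - pP) * x.

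| pA / pP | Diaries lost of 120 | x = 1 | x = 2 | x = 3 | pA * 1.79 |
|---|---|---|---|---|---|
| 2.6% / 1% | about 3 v 1 | 0.016 | 0.032 | 0.048 | 0.047 |
| 5% / 2% | about 6 v 2 | 0.03 | 0.06 | 0.09 | 0.090 |
| 10% / 4% | about 12 v 5 | 0.06 | 0.12 | 0.18 | 0.179 |

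The range 0.016 to 0.18 is 1% to 10% of 1.79, or 0.04 to 0.40 standard errors. For volume, an assumed fall of 10 to 40 mL gives 0.016 x 10 = 0.16 mL to 0.06 x 40 = 2.4 mL, under 1% to 8% of 30 mL. Extra automatic non-response on active is at most pA - pP, or 1.6 to 6 percentage points.

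The bottom row is extreme. It needs 0.10/0.264 = 38% of active and 0.04/0.101 = 40% of placebo patients who ever have a UTI to lose this one diary.

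**4. Power under the current rule**

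In the bottom row, 108 active and 115 placebo diaries remain. At 1.79 and SD 3.5 the power is 96.7%, against 97.6% with none lost. (At an effect of 1.79 - 0.18 = 1.61 with all 120 per arm it is 94.4%, but that describes an analysis that uses the symptomatic diaries, not the current rule.)

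**5. What the planned sensitivity analysis covers**

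The last column of the table is the most that placebo-based imputation can pull the effect towards zero, if imputed active patients take the placebo mean. The ceilings 0.047, 0.090 and 0.179 sit beside the x = 3 values 0.048, 0.09 and 0.18. Because the model conditions on earlier visits, the actual shift would be smaller. It is a stress test in the right direction, not a guaranteed bound.

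**The case for a change.** The strongest reply is that the planned analyses process the blank but cannot test dependence on UTI. UTI status is not in the MMRM, the imputation model is fitted to placebo data from which symptomatic diaries are also withheld, and its shift is governed by the treatment effect rather than by infection. Collecting and flagging these diaries, setting them to missing in the primary analysis and running the alternative beside it would cost little and would show the answer. All of that is true as description.

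It does not amount to a fault. The effect is overstated only if the target is the outcome with UTI-affected days included as recorded, and the protocol deliberately rejects that target. For bladder symptoms free of infection, leaving those days out is not in itself bias.

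Collection also has a cost. A patient whose symptoms clear may still give a clean diary between Day 65 and Day 106. If the symptomatic diary were collected as well, SAP 11.6.3 starts from the first episode in the window and SAP 11.6.1 takes the value nearest the target day, so the infected diary could displace the clean one unless a precedence rule were written. Adding 1 to 3 episodes/day to imputed values instead would do nothing for volume, and would need a reason for each blank that the documents do not show being recorded.

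What stands is a matter of labelling: SAP 7.1.4 could say that diaries withheld for UTI are treated as missing, and a count by arm and visit would help a reader. Results are sound without either.

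**Conclusion.** No change is needed. Protocol 7.3.1.1 makes a reasoned choice, the SAP's general rules carry it through every diary-based analysis, and different handling across endpoints and supporting analyses is ordinary practice. SAP 2.1 gives its reason for scoring missing responders as failures, and SAP 11.1.1 says the incomplete-diary exclusion is not a deviation.

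On assumed inputs the primary effect differs by 0.02 to 0.18 episodes/day from one using all diaries as recorded, and power stays near 97%. The upper end needs about 40% of patients who ever have a UTI to lose the Week 12 diary and each UTI diary to hold 3 extra episodes/day. That is hard to reach when one valid day in a 42-day window is enough (106 - 65 + 1 = 42), visits have a 7-day allowance either side and missed visits are rescheduled. The 26.4% and 10.1% are themselves only a rough guide, since the pool includes an extension study and this trial counts UTI without symptoms as an adverse event. The true loss by arm is unknown from the documents, but no plausible value threatens the conclusion.

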### **7.3.1.2. Health outcome questionnaires**

The subject's perception of the level of impairment in work and other regular daily activities, etc. associated with the symptoms of OAB with urinary incontinence will be assessed using patient-completed questionnaires as specified below. Questionnaires should be administered in accordance with the study schedule and prior to study treatment on initiation of Treatment phase 1 (week 0). The investigators / subinvestigators or the persons assisting with the trial will ensure that the subjects answer all the questions. The questionnaires will be treated as source documents and archived with the medical record.

#### **7.3.1.2.1. King's Health Questionnaire (KHQ)**

Impact of urinary incontinence on QOL will be assessed using KHQ in accordance with the study schedule.

KHQ was developed by Kelleher et al. as questionnaire to assess impact of urinary incontinence on QOL. [Kelleher, 1997] The HQ was translated into Japanese by Honma et al., and its appropriateness was verified in Japanese patients with urinary incontinence. [Honma, 1999; Honma, 2002]

KHQ is a questionnaire with 21 items and consisted by 9 domains: (i) General health, (ii) Incontinence impact, (iii) Role Limitations, (iv) Physical limitations, (v) Social limitations, (vi) Personal relationships, (vii) Emotion, (viii) Sleep/energy, (ix) Severity measure. The scores are summated according to an algorithm provided by Kelleher et al. [Kelleher, 1997]

Investigators/subinvestigators or the persons assisting with the trial will provide a KHO questionnaire and instruct subjects to select the one most appropriate answer for each question.

